2.4.2 Hypothesis

Delivery of DEB-TACE with the Surefire Precision Infusion System in patients with HCC who are being considered for liver transplant and are being treated for the purpose of tumor down-staging results in improved tumor response (mRECIST criteria) at 1 month as shown by contrast enhanced CT/MRI as compared to matched historical control patients who received DEB-TACE delivered with a standard endhole catheter.

2.4.3 Primary Endpoints

1. Tumor response (modified RECIST criteria) at 1 month as shown by contrast enhanced CT/MRI. (Note: Tumor response will be determined on a per-treated lesion basis.)
2. Local recurrence rate (LRR) at 6 months as shown by contrast enhanced CT/MRI
3. Absolute Tumor enhancing maximum diameter at 1M and 6M.

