3.3 Sample Size

Fifty (50) subjects will be enrolled in the prospective arm.

Data from one hundred (100) historical randomly sampled control subjects (1:2 ratio) will be selected.

The statistical basis for the sample size is provided in Section 4.3.

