4.3 Justification of Sample Size

The sample size for this study is based on the primary outcome of local recurrence rate (LRR). We conducted a power analysis to assess detectable difference in proportion recurring and the associated power for a Fisher' exact test. The test can be conceptualized by the following two by two table (2x2 plus margins are presented). We will test the null hypothesis of no difference in the proportion of patients with local recurrence by catheter type.

Tumor recurred	Endhole catheter	Precision catheter	Total
Yes	30 expected	?	30 + ?
No	70 expected	?	70 + ?
Total	100	50	150

Based on the existing literature, we expect our historical controls (endhole catheter) to have a local recurrence rate of 30%.³ The following table presents some possible scenarios for power and sample size. All of these estimates assume a 30% LRR in the control group and a type I error rate of 0.05. We have included sample sizes for the pilot phase of the study in the table below.. The pilot study will also include an interim analysis after treating at least 20 patients with the precision catheter. At this point we will compare the proportions of LRR in the control and comparison groups; although we do not expect statistical differences in LRR between the two groups due to low power, the funder has asked that we provide these data. This interim analysis will be solely used to provide a brief progress report to the funder; these interim data will not be published, nor will they be applied to any stopping rules for the study.

The data generated in this pilot study will be used to estimate power and sample size for a multicenterclinical trial.

Expected LRR: Endhole catheter	Expected LRR: Precision catheter	Detectable difference (absolute difference)	Type I error rate (alpha)	Power (1-beta)	N control group (Endhole catheter)	N comparator group (Precision catheter)
Pilot Phase						
30%	25%	5%	0.05	0.07	100	50

³ Thirty percent was selected as an anticipated amount to see an improvement in care. This seemed reasonable, given the current efficacy of therapy.

30%	20%	10%	0.05	0.21	100	50
30%	15%	15%	0.05	0.47	100	50
30%	10%	20%	0.05	0.78	100	50
Interim pilot phase analysis						
30%	25%	5%	0.05	0.05	100	20
30%	20%	10%	0.05	0.10	100	20
30%	15%	15%	0.05	0.21	100	20
30%	10%	20%	0.05	0.41	100	20

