4.4 Statistical Analysis Plan

All statistical tests use a type I error rate of 0.05. We will calculate descriptive statistics for all variables of interest including means, medians and standard deviations for continuous measures, and frequencies and percents for categorical variables. These calculations will be performed overall and stratified by treatment assignment. We will compare baseline characteristics between the treatment and retrospective groups. We will test for differences using independent samples t-tests (alternatively, Wilcoxon-Mann-Whitney tests if data are skewed) for continuous variables, and Chi-square tests (alternatively Fisher's exact tests if some cells are sparse) for categorical variables.

For the outcome of local recurrence rate (LRR) we will test the null hypothesis of no difference in the proportion of patients with local recurrence by catheter type using a Fisher's exact test.

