For the outcome of tumor response measured as the change in enhancing tumor size (pretreatment – post treatment) we will evaluate changes at 1 month and 6 month separately. We will calculate the difference in tumor enhancement size at 1 month and 6 months using enhancement size at initial treatment as the reference group (i.e. we will have two continuous outcomes which can be positive or negative values). The analyses are exactly parallel for 1 month and 6 month outcomes. We will describe the approach for 6 months. We will fit a general linear model with Kenward-Roger denominator degrees of freedom. The outcome will be the first-differenced 6 month tumor enhancement size. We will use a random intercept to account for correlation between lesions within a given patient. The independent variables will include catheter type, age and sex. We will test the null hypothesis of no association between catheter type and change in tumor enhancement size. In the case that this model fails to converge, or in the case that most patients have only one tumor, we will use an alternative approach. In this alternative approach we will sample one lesion per patient and use ordinary least squares regression and include age and sex as covariates with catheter type as the primary predictor of interest. We will test the null hypothesis of no association between change in tumor enhancement size and catheter type. Should this model also fail to converge, we will simplify further and use a paired t-test comparing initial and 6 month tumor enhancement sizes in a sampled data set (i.e. one tumor per patient), or we will use a Wilcoxon-Mann-Whitney test if the sizes are skewed. We will test the null hypothesis of no association between catheter and tumor enhancement size change.

For the outcome of time to progression, we will quantify the number of weeks from treatment until tumor progression. Failures (or events) will be defined as progression of the tumor per CT examination or AFP level and extrahepatic disease by CT examination, or death due to complications related to the tumor. Censored observations will be defined as patients who we did not observe tumor progression, patients who were lost to follow up, or patients who had a

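### Primary endpoint 3 is a diameter at 1 and 6 months in 2.4.3 but a change from pretreatment in 4.4, and without adjustment for pretreatment size the two can point in opposite directions

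*Combined protocol and SAP*

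**What the plan says.** Section 2.4.3 lists three primary endpoints. The first is mRECIST tumor response at 1 month, per treated lesion. The second is local recurrence at 6 months. The third is "Absolute Tumor enhancing maximum diameter at 1M and 6M", which is a level at two time points. The Study Summary in 1.2 lists only the first two.

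The continuous size analysis in 4.4 opens "For the outcome of tumor response measured as the change in enhancing tumor size", defined there as pretreatment minus post-treatment. It is run separately at 1 and 6 months. For the 6-month model, "The outcome will be the first-differenced 6 month tumor enhancement size". On covariates: "The independent variables will include catheter type, age and sex". A random intercept handles several lesions in one patient, and the first fallback is ordinary least squares on one sampled lesion per patient with the same covariates. No between-catheter model in 4.4 has the diameter itself as outcome, and none includes pretreatment size.

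On the comparison group, 2.4.1 and 3.1 speak of matched historical controls, while 3.3 says 100 controls will be randomly sampled. No matching variables are given.

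**The concern.** The quantity named as primary is not the quantity modelled, and the modelled quantity carries the name of a different primary endpoint. A reader of the results could not tell whether a reported size difference answers endpoint 1, endpoint 3 or neither.

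In a randomised trial this would be mostly untidy, because level and change would share the same expected treatment effect. Here the controls are historical, and the two definitions separate as soon as the groups differ in pretreatment size. The same scans could then be reported as showing the device worse (larger residual diameter) or better (more shrinkage), with no difference between the catheters.

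**Working it through.** **Plan figure.** The plan gives no power, SD or expected difference for any diameter endpoint. Its only power figures, in 4.3, are for local recurrence: "We will test the null hypothesis of no difference in the proportion of patients with local recurrence by catheter type". They reproduce: for 30% against 10% with 100 and 50 patients, the Walters arcsine approximation to two-sided Fisher power gives 0.778 against the stated 0.78. They are not affected by this point.

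**Step 1: how the two definitions relate.** Write P for pretreatment size, L for the level after treatment, C = P − L for the change, and Δ for device mean minus control mean. Then

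ΔC = ΔP − ΔL.

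If ΔP = 0, the two comparisons are equal apart from sign. If ΔP > 0, the baseline difference is divided between a larger residual (against the device) and a larger shrinkage (for the device).

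**Step 2: is ΔP = 0 secured?** The pool in 2.4.1 is all patients treated at the centre since 2009 with 100–300 micron beads and with follow-up: 84 of 152 (55%) at 0–3 cm and 129 of 152 (85%) below 5 cm. The Study Summary describes device patients as outside Milan, although inclusion criterion 3 in 3.5.2 also admits patients within it. Larger device tumours are plausible but not certain. Nothing in the model corrects for them.

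**Step 3: direction.** Inputs from 2.4.1 are the size ranges and 1-month response counts per band, leaving out the one patient lost to follow-up. Assumptions: size uniform within each range; viable ratio L/P of 0 for CR, 0.1–0.7 for PR, 0.7–1.2 for SD and 1.2–1.5 for PD (means 0, 0.4, 0.95, 1.35).

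| Band | Mean P (cm) | Mean ratio | Mean L | Mean C |
|---|---|---|---|---|
| 0–3 cm | 2.15 | (32×0.4 + 14×0.95 + 5×1.35)/84 = 0.391 | 0.84 | 1.31 |
| 3–7 cm | 5.10 | (39×0.4 + 4×0.95 + 1×1.35)/59 = 0.352 | 1.79 | 3.31 |
| >7 cm | 12.30 | (6×0.4 + 1×0.95 + 1×1.35)/8 = 0.588 | 7.23 | 5.07 |

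Both residual and shrinkage rise with size, so a larger-tumour group looks worse on level and better on change.

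**Step 4: size, with identical catheters.** With the pool's mix (84/60/8), control means are P 3.85, L 1.55 and C 2.30. With an assumed device mix of 20/60/20%, the means are P 5.95, L 2.69 and C 3.26. So ΔP = 2.10, ΔL = 1.14 and ΔC = 0.96, and 1.14 + 0.96 = 2.10 as Step 1 requires. With 100 controls and 50 device patients, and SDs from a simulation under the same assumptions:

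- Level: 1.14/√(2.21²/100 + 3.48²/50) = 1.14/0.54 = 2.1, against the device.
- Change: 0.96/√(2.09²/100 + 2.86²/50) = 0.96/0.455 = 2.1, in its favour.

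Other assumed device mixes, with controls unchanged (a cap limits the device group's largest tumours):

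| Device mix (0–3/3–7/>7 cm) | Largest device tumour | z, level (against) | z, change (for) |
|---|---|---|---|
| 20/60/20% | 17 cm | 2.1 | 2.1 |
| 20/60/20% | 12 cm | 1.9 | 1.9 |
| 20/60/20% | 8 cm | about 1.5 | about 1.6 |
| 30/60/10% | 17 cm | 1.1 | 1.5 |
| 40/50/10% | 17 cm | 0.9 | 1.0 |

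The directions are opposite in every row. Both exceed 1.96 only in the first.

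**Step 5: adjusting for P.** If L = a + b·catheter + c·P + other terms, then C = P − L = −a − b·catheter + (1 − c)·P − other terms. The catheter coefficient is b for the level and −b for the change, with the same standard error. This holds for the mixed model and for ordinary least squares, so the choice of definition no longer affects the result.

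**The case against.** The strongest reply is that this is ordinary drafting. 'Absolute' may mean centimetres as opposed to the percentage-based mRECIST categories, and 4.4 does analyse enhancing size in absolute units at exactly 1 and 6 months. That has force. Linking the 4.4 model to endpoint 3 is an inference, and a reader who concludes that endpoint 3 was simply forgotten goes further than the text allows. But the endpoint is worded as a diameter at two times, with no mention of change, and 4.4 gives its model the name of endpoint 1. On either reading the two sections need reconciling.

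A second reply is that the harm shown is confounding by tumour size, and that matching may deal with it. Matching on size would reduce it, but no matching variables are given and 3.3 describes random sampling. With equal baselines, simulations (SD 2 cm, true advantage 1 cm, correlation 0.3 to 0.8) gave no significant results in opposite directions, yet the two tests still disagreed on significance in 18 to 26% of trials.

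Three stronger readings are tempting and are not supported:

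- **That one definition has less power.** With equal SDs s and correlation ρ, the SD of the change is s√(2(1−ρ)), below s only when ρ exceeds 0.5. The documents give neither s nor ρ. In the simulation, the order reverses when an assumed proportional effect is replaced by a fixed shift.
- **That the change score mainly reflects baseline size.** In the simulation, baseline correlates more with the level (0.64) than with the change (about 0.59).
- **That opposite significant results are to be expected.** They appear only with an assumed mix containing many very large tumours. The dosing table in 3.8 lists diameters only up to 8 cm.

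The calculation covers 1 month only. The 6-month comparison is further affected by the rule in 3.11 on residual disease.

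**Conclusion.** The mismatch is in the current text and rests on no simulation: a primary endpoint is defined as a level, and the only continuous size model analyses a change, under another endpoint's name and without pretreatment size.

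Its consequence is conditional. If device patients have larger tumours than controls, the unadjusted level is biased against the device and the unadjusted change in its favour, and the two biases add up to the baseline difference. Under the assumed mixes, z ran from about 0.9 to 2.1 in opposite directions with identical catheters. This depends on the assumed device size mix, the assumed viable ratios and one lesion per patient. If pretreatment size is balanced, the bias disappears and only the wording conflict remains.

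The change should be made, with modest weight: the study is a pilot sized on local recurrence, and the Study Summary omits this endpoint.

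**What to change.** Use one definition in both places.

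- In 2.4.3, state endpoint 3 as enhancing maximum diameter at 1 and 6 months, compared between catheters with adjustment for pretreatment enhancing diameter.
- In 4.4, make that diameter the outcome and add pretreatment enhancing diameter to catheter type, age and sex, both in the mixed model and in the one-lesion least-squares fallback.
- Remove the label tumor response from this analysis, so that it is not read as endpoint 1.

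The cost is wording and one extra covariate. Pretreatment size is already needed to form the current first difference, so closure of the study on 18 June 2018 is no obstacle. The change should be dated before the size data are analysed. Linear adjustment reduces confounding by size in a non-randomised comparison but does not guarantee its removal. Pretreatment diameter by group should therefore be reported beside the result.

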2.4.4 Secondary Endpoints

1. Tumor response (mRECIST criteria) at 3 and 6 months as shown by contrast enhanced CT/MRI
2. Successful downstage to Milan criteria or UCSF criteria
3. Time to progression
4. Treatment-related toxicity
5. Change in Liver Functions Tests
6. Change in Quality of life
7. Changes in AFP levels

3. STUDY DESIGN

3.1 Study Design

This is a single institution prospective clinical trial with historical matched controls.²

This protocol standardizes DEB-TACE delivery with the Surefire Precision Infusion System.

This protocol does not change patient therapy as the Surefire Precision Infusion System is a standard of care device. All patient safety monitoring, treatment procedures and follow-up procedures will be performed in accordance with standard clinical practice.

3.2 Study Sites

The study will be performed by the Division of Interventional Radiology at the University of Colorado Hospital.

3.3 Sample Size

Fifty (50) subjects will be enrolled in the prospective arm.

Data from one hundred (100) historical randomly sampled control subjects (1:2 ratio) will be selected.

The statistical basis for the sample size is provided in Section 4.3.

3.4 Study Duration

The study was closed by the sponsor on June 18, 2018. All screening, data entry and follow-up visits were ceased on this day. Adverse event follow-ups are still occurring, and are outlined in more detail in Section 4.6.

3.5 Subject Selection (Eligibility)

Patients will no longer be screened for this study as of 06/18/2018.

3.5.1 Recruitment Population

Patients with HCC that are being evaluated for liver transplantation and scheduled to receive DEB-TACE treatment for tumor down-staging.

No advertising will be done for the purpose of recruitment since patients are routinely referred to the transplant center for evaluation. All consecutive patients who meet the eligibility criteria will be approached to assess for interest in participating in the study. Patients who are not interested in participating will receive treatment with either standard TACE or the SUREFIRE system, depending on the treating physician's prerogative, since both are FDA approved.

3.5.2 Inclusion Criteria

1. Patients aged 18 years or older with the diagnosis of HCC currently being evaluated for liver transplantation and considered for downstaging.
2. Patients undergoing Surefire DEB-TACE procedure as clinically determined to be part of their standard of care treatment plan.

² In order to test the hypothesis (section 2.4), this prospective study has been designed for eligible participants to receive DEB-TACE with the Surefire Precision Infusion System. Historical matched patients, who previously underwent the DEB-TACE using a standard endhole catheter, will serve as the control group for this study (section 3.1). Given the lack of available comparator data, it is most appropriate to gather the data single arm and with the data develop an appropriate statistical framework for comparison.

3. Meets Milan criteria: a single tumor that is < 5cm or a maximum of 3 tumors with each tumor <3cm AND/OR meets UCSF criteria: a single tumor that is < 6.5 cm in diameter or 2 lesions < 4.5cm with total tumor diameter <8 cm AND/OR is outside of both Milan and UCSF criteria and is being evaluated for downstaging.
4. No portal invasion or extrahepatic spread.
5. No previous chemotherapy, radiotherapy or transarterial embolization (with or without chemotherapy).
6. Eastern Cooperative Oncology Group (ECOG) performance status of 0 or 1.
7. Preserved liver function (Child-Pugh Class A or B).

3.5.3 Exclusion Criteria:

1. Advanced bilirubin levels > 3 mg/dl
2. INR > 2 in the absence of anticoagulation therapy
3. AST or ALT>5 upper limit of normal or >250 U/l
4. Advanced tumoral disease, defined as vascular invasion, extrahepatic spread, or diffuse HCC (50% liver involvement)
5. Contraindications for doxorubicin administration.
6. Child's Class C

3.6 Informed Consent

No more patients will be consented for this study as of 06/18/2018.

Eligible study subjects will be provided with a study overview and written informed consent form to review.

Only patients that sign the informed consent form will be enrolled in the study. The form is dually signed by the person who conducted the informed consent discussion.

3.7 Baseline / Pre-Treatment Procedures

No more patients will undergo baseline / pre-treatment procedures as of 06/18/2018.

The following evaluations/activities will be performed at baseline:

- Informed Consent
- Medical history
- Physical Exam
- Data Collection of Standard of Care CT/ MRI within 1 month of the visit date.
- Data Collection of Standard of Care Lab Values including CBC, CMP, AFP and INR.
- Quality of Life Questionnaire

3.8 Treatment Procedures

No more patients will undergo treatment procedures as of 06/18/2018.

All patients enrolled in this protocol will receive DEB-TACE, which is the standard of care prescribed by their physician.

Lactate whole blood venous will be collected prior to procedure.

Standard 5 Fr and 3 Fr catheters will be used to perform diagnostic angiography to map the hepatic vasculature to the tumor. Using standard technique, the target vessel feeding the tumor will be catheterized and DEB-TACE administered using the Surefire Precision catheter.

The Doxorubicin dosing used in the DEB-TACE will be based upon tumor volume as follows:

Doxorubicin Dosimetry by Tumor Volume		
Tumor Diameter (cm)	Tumor Volume (cc)	Doxorubicin (mg)
3	14.14	75
4	33.51	75
5	65.45	100
6	113.10	150
7	179.59	150
8	268.08	150

DEB-TACE will be administered until the first of the following endpoints is reached:

- Achievement of target dose with stasis
- Leeching of contrast through the expandable tip
- Development of distal intrahepatic collaterals

Note: In hypervascular tumors, the additional use of bland spheres may be needed to achieve the DEB-TACE delivery endpoint.

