2.3 Clinical Rationale

In summary, current techniques for down-staging patients for OLT into Milan Criteria is hindered by several vital issues:

- Poor conversion rates
- High recurrence rates
- Variable delivery techniques
- Variable dosimetry.

The aims of bridging treatments include decreasing the waiting list dropout rate before transplantation, reducing HCC recurrence, with the goal of standardizing dosimetry and delivery methods. To date, no data from prospective randomized studies are available to support these aims.

Despite the effectiveness of DEB-TACE for the treatment of primary malignancy, this procedure is limited by the lack of a consistent endpoint for therapy. The dosage and delivery mechanism is

not standardized and often patients often have to undergo multiple procedures with varying dosages to effectively control the tumor.

Thus, this research protocol will provide critical information on how to perform DEB-TACE in patients undergoing down-staging protocol for OLT. By proving our hypothesis, we envision that this procedure may improve outcome of therapies and minimize repeat treatments by providing a consistent standard of therapy.

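### The comparison is Surefire plus a dosing and endpoint protocol against earlier end-hole practice, but the hypothesis and the recurrence test credit any difference to the catheter

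*Combined protocol and SAP*

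**What the plan says.** **Surefire arm.** Section 3.1 states: "This protocol standardizes DEB-TACE delivery with the Surefire Precision Infusion System". Section 3.8 adds: "The Doxorubicin dosing used in the DEB-TACE will be based upon tumor volume as follows". A table follows, running from 75 mg at 3 cm to 150 mg at 8 cm. Delivery then stops at whichever of three listed endpoints comes first. One of these, contrast escaping through the expandable tip, cannot occur with an end-hole catheter. Section 3.11 applies the same procedures to retreatment.

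**Controls.** Section 2.4.1 defines them by hospital, period (since 2009), bead size and available follow-up. It sets no condition on dose or delivery endpoint. Sections 2.4.1, 2.4.2 and 3.1 call them matched. Section 3.3 says "Data from one hundred (100) historical randomly sampled control subjects (1:2 ratio) will be selected", and no matching variable is listed.

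**Existing practice.** Section 2.3 says that dosage and delivery in DEB-TACE are "not standardized and often patients often have to undergo multiple procedures with varying dosages to effectively control the tumor". Section 2.1.5 describes stopping at stasis or substasis through an end-hole catheter as subjective and without a measurable endpoint.

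**Analysis.** Section 2.4.2 credits the expected improvement to delivery with the Surefire system. Sections 4.3 and 4.4 test the null hypothesis of "no difference in the proportion of patients with local recurrence by catheter type" with an unadjusted Fisher's exact test. The tumour-size model in Section 4.4 contains catheter type, age and sex. The Cox models contain treatment group, age, sex and a stage/severity variable.

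**The concern.** Up to three things may change together between the groups: the catheter, the rule for the drug dose, and the rule for ending delivery. The planned tests see only group membership, so they cannot tell these apart. Section 2.3 itself expects a consistent standard of therapy to improve outcomes and reduce repeat treatment. Standardisation is thus a rival explanation that the protocol names.

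What is at stake is the meaning of a positive result. A recurrence difference would be reported as a catheter effect, although part or all of it could come from how dose and endpoint were set. Section 4.3 says the data will be used to size a multicentre trial, so the label would carry forward.

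Section 3.1 also says both that the protocol standardises delivery and that it leaves patients' treatment unaltered. The second statement is hard to square with Section 3.8 unless the hospital already dosed and stopped this way, and the documents do not say so.

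**Working it through.** **1. What differs by group, and what the analysis uses**

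| Element | Surefire arm | Controls | In any analysis? |
|---|---|---|---|
| Catheter | Surefire Precision (3.8) | Standard end-hole (2.4.1) | Yes, as group |
| Doxorubicin dose | Table by tumour size, 3 to 8 cm (3.8) | Not reported; no condition set (2.4.1) | No |
| Delivery endpoint | First of three listed (3.8) | Not reported; general practice is stasis or substasis (2.1.5) | No |
| Treatment period | Prospective | Since 2009 (2.4.1) | No |

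Only the first row is named in the hypothesis and in the recurrence null hypothesis.

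**2. The plan's own power figure**

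Inputs from Sections 3.3 and 4.3: "Fifty (50) subjects will be enrolled in the prospective arm", 100 controls, and "All of these estimates assume a 30% LRR in the control group and a type I error rate of 0.05". Sidedness is not stated; two-sided is assumed here. The continuity-corrected arcsine approximation to Fisher's test is

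power = Φ( 2[arcsin√(p1 − 1/(2n1)) − arcsin√(p2 + 1/(2n2))] / √(1/n1 + 1/n2) − 1.96 ).

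For 30% versus 10%, with n1 = 100 and n2 = 50:

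- arcsin√0.295 = 0.5742 and arcsin√0.110 = 0.3381, difference 0.2361
- 2 × 0.2361 / √0.03 = 0.4722 / 0.1732 = 2.726
- Φ(2.726 − 1.96) = 0.778, against 0.78 stated.

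With both tails counted, this method matches all eight rows of the table to two decimals. The power table is not in error. The point concerns what a rejection means.

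**3. Illustration under an assumption**

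The documents give no size for a dosing or endpoint effect. Assume that the catheter has no effect and that non-catheter factors alone lower recurrence in the Surefire arm by s points from 30%. Then

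P(reject) = Σa Σb Bin(a; 100, 0.30) × Bin(b; 50, 0.30 − s) × 1{Fisher p ≤ 0.05},

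computed by full enumeration with two versions of the two-sided Fisher test:

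| s (points) | Equal-tailed | Minimum-likelihood |
|---|---|---|
| 0 | 0.0323 | 0.0400 |
| 5 | 0.0658 | 0.0785 |
| 10 | 0.1973 | 0.2251 |
| 15 | 0.4589 | 0.5019 |
| 20 | 0.7799 | 0.8137 |

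The excess over no difference is 0.0658 − 0.0323 = 0.034 (or 0.0785 − 0.0400 = 0.039) at 5 points. At 10 points it is 0.1973 − 0.0323 = 0.165 (or 0.2251 − 0.0400 = 0.185). These are ordinary power values for a difference of that size. They show that the test responds identically whatever the cause.

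**4. Could the groups be compared at equal dose?**

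The dose table starts at 3 cm, while 84 of the 152 in the historical table (84/152 = 55%) are in the 0-3 cm class. Section 3.11 removes patients with residual disease at one month from the six-month recurrence evaluation. If controls follow that rule, the 3-7 cm class offers 15 complete responders, of whom 3 were lost, leaving 15 − 3 = 12. The class above 7 cm offers none. Apart from any controls at exactly 3.0 cm, a dose-matched subset would be drawn from about a dozen patients.

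**The case against.** The strongest reply is in Section 2.2.1: by eliminating reflux, the catheter is said to make it possible to fit the dose to tumour size rather than to flow. On that view size-based dosing is part of what the device delivers, and dose lies on the pathway of its effect. This stands, and it is why dose should not be adjusted away. But it argues for naming the strategy as the thing compared; it does not support a claim about catheter type alone.

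Second, a reader might infer that the controls are known to have received unstandardised doses. The documents do not support that. Sections 2.1.5 and 2.3 describe practice in general, and no section reports the dose rule or endpoint used for these controls. Section 3.1 says procedures follow standard clinical practice, so the hospital may already have dosed by size. If it did, the dose part of the concern shrinks.

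Third, the dose in the Surefire arm is not wholly fixed either. Two of the three endpoints can end delivery before the target dose, and the table covers 3 to 8 cm only.

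Fourth, Section 4.3 calls this a pilot, and a footnote to Section 3.1 says the data will help develop a framework for comparison. If the multicentre trial uses the same package, the package effect is the right planning input. That holds provided it is labelled as such.

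**Conclusion.** The point holds as one of attribution. The Surefire arm receives a catheter together with dosing and endpoint rules. The controls were selected without regard to either rule, and no analysis uses dose or endpoint. The design can estimate the effect of the combined strategy against earlier end-hole practice, and a rejection cannot be credited to the catheter alone.

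The size of any non-catheter contribution cannot be obtained from the documents. The range of about 7-8% to 20-23% rejection, against 3-4% with no difference, rests on an assumed effect of 5 to 10 points, a 30% control rate and two-sided testing. A reader might take it as this trial's false-attribution rate; the documents do not support that, because they give neither the control doses nor the size of a dosing effect. Nor does the point show that the stated power is wrong.

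**What to change.** - **Reword the comparison.** In Sections 2.4.2, 4.3 and 4.4, and in any conclusion, state it as *Surefire delivery under this protocol's dosing and endpoints versus end-hole DEB-TACE as previously practised*. Make no catheter-only claim.
- **Describe what was given.** From existing procedure records, where available, tabulate delivered doxorubicin, delivery endpoint and treatment year by group within tumour size class, as description only.
- **Do not add a sensitivity analysis restricted to dose-matched controls**, and do not let the wording of the conclusion depend on one. Delivered dose is a post-treatment quantity, limited by flow with end-hole catheters (Section 2.1.5), so selecting on it can introduce bias. The usable subset would also be very small. Where an endpoint exists in one group only, no adjustment can separate the effects.
- **Reconcile** the Section 3.1 statement that therapy is unaltered with the standardised delivery in Sections 3.1 and 3.8. No dose or clinical rule is proposed here.

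The cost is a narrower claim, some changes of wording and some chart abstraction. The abstraction is limited by the June 2018 closure and the end of data entry (Sections 3.4 and 4.6). The rewording is not, and it also applies to the planning of the multicentre trial.
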